Participants will access the study via an online link provided by email or via word of mouth. They will first answer a question to assess their suicide risk. If they have not had suicidal thoughts in the previous three weeks, they will continue on to the study. If they indicate they have had such thoughts in the prior three weeks, they will be disqualified from the study and a screen will appear with contact information regarding mental health resources. [name] will then reach out to Student Counseling Services and ask them to reach out to the students to follow-up and provide additional support. For those students who continue with the study, they will take the PHQ-9 and the GAD-7 to measure their depression and anxiety levels. If they score 5 or above on either test they will be invited to participate in the therapy part of the study. In this part of the study the participant will be assigned to either receive individual teletherapy or group teletherapy for 12 weeks. This therapy takes place via text. Participants may be asked to read psychoeducational materials and complete homework assignments. Participants assigned to the individual therapy, will receive support in the form of direct asynchronous communication with the therapist. Participants assigned to the group therapy will receive support in the form of direct asynchronous communication with the therapist and asynchronous communication with peers struggling with similar issues. Throughout the at week 4, 8 and 12 of therapy, participants will take the GAD-7, PHQ-9, and self-report questionnaires to measure their engagement and experience.

Describe the location where research activities will take place:

The research will take place on participants personal electronic devices by logging on to the web-based TheraGroup platform. TheraGroup is a proprietary real-time virtual based platform that provides text based group therapy. It is a cloud software that offers HIPAA compliant asynchronous text chat.

How long will the participants be engaged in research? (length of time, i.e. 15 minutes on day 1, etc.):

up to 12 weeks

During data collection, describe what steps will be taken to ensure participant privacy:

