The current mental health crisis across college campuses particularly impacts students at Historically Black Colleges and Universities (HBCUs), who, compared to their Predominantly White Institution (PWI) counterparts, have fewer resources and less funding to support student psychological health [1]. While online therapy offers benefits, it does not solve the issue that the number of available therapists is insufficient to treat the number of students seeking help [2]. A promising solution is to increase opportunities for group therapy, which is equivalent to individual therapy in terms of outcomes [3]. As such, the purpose of our study is to assess the impact of an online, group text based therapy (one mental health counselor to many students) against a one-to-one (one mental health counselor to one student) therapy among HBCU students. Specifically, we will compare a HIPPA compliant, guided group telehealth (GGT) therapy (group therapy) called TheraGroup against a HIPPA compliant individual telehealth (IT) therapy (individual therapy) on measures of engagement, user experience, and mental health outcomes. If outcome measures in the GGT group are in line with outcome measures in the IT group, the feasibility study will serve as a precursor to testing the effects

RISKS AND BENEFITS

Describe any potential risks or discomforts to the participant (including physical, psychological and/or social):

Risks to subjects are rated as "Low", "Medium", "High". Do not say "none".

participants may be at risk of psychological harm. As the survey measures and therapy intervention ask participants to explore their mental health, specifically difficulties they may be having and traumatic events they have previously experienced, this process may exacerbate pre-existing mental health

Describe any potential benefits to the research participant or society:

Participants in this study will benefit from receiving mental health treatment from qualified professionals. Identifying effective group telehealth therapies to increase the access to mental health interventions contributes not only to the expansion of scientific knowledge within the field of mental health, but also to practical applications. Based on the findings of this study, interventions, trainings, and supports can be developed to treat mental illness in Black college students. This has potential

Describe alternatives to participation/opportunity to withdraw:

Participants may withdraw at any time

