SUBJECT RECRUITMENT

Number of participants (target population): 8000 Ages of Participants: 18 years or older

Gender of subjects: Male

Maximum anticipated sample size: 200

Female

What are the selection criteria for participation (i.e. include target population and maximum anticipated sample size)?
For clarification on target population and maximum anticipated sample size, please refer to FAQ #35 on the [PVAMU IRB website](#).

Participants must be Black college students attending Prairie View A&M University (PVAMU) who are at least 18 years of age, and who qualify for psychological clinical intervention based on their current levels of depression and anxiety.

Do the criteria for selection exclude individuals based on gender, culture, language, economic status or ethnicity?

Yes No

If yes, please justify exclusion:

We are excluding non-Black individuals. The telehealth program we are testing is tailored for the Black population and thus we would like to test it on a matching sample.

Are there any special physical or psychological conditions of subjects? (If so, please describe.)

Participants who score a 5 or more on the GAD-7 (anxiety) or the PHQ-9 (depression) will qualify for the therapeutic intervention aspect of the study. These scores represent at least a minimal level of anxiety and depression.

Source of participants:

PVAMU students (provide explanation below) Community (provide explanation below)
 Schools* (provide explanation below) Other (provide explanation below)

Participants will be Black college students attending PVAMU

For studies involving schools:

Does the study involve a school district? Yes No

If Yes, which school district(s): _____

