Due to the longitudinal design of this project, collecting identifiable data is necessary. Specifically, participants' names and contact information are needed to match participant information at different time points and to contact participants about distributing their gift card compensation. In order to preserve participant confidentiality and minimize the potential harm of participant information being identified, participants' will be prompted to create an identification number comprised of the first two letters of their last name combined with the last four digits of their phone number (e.g., Jane

Is the research anonymous or confidential? (**Cannot be both**)

Anonymous: The identity of the participant cannot be readily determined by the investigator AND the identity of the participant is not connected to information gathered.

Confidential: Research participants can be identified; however, information gathered will be protected.

Provisions for anonymity/confidentiality:

Secure storage (**required**)

Replies coded

What specific steps will be followed to ensure anonymity or confidentiality of participants' responses?

The participant ID and identifying information (name-code-index) as described above will be stored on a password protected spreadsheet. Only [name] and her team will have the ability to de-identify participants. Disclosure of data via research dissemination methods such as presentations at conferences and in study related publications will not contain identifying information. In addition, for the group therapy, participants use a name they make up for the purpose of the group only to ensure they remain anonymous. The therapy contains no face to face modalities. It all occurs via text based communication.

DATA COLLECTION

Research Type:

- Qualitative
- Quantitative
- Both

Will any new data or documents be collected? (i.e. *public records, survey instruments, evaluation tools, etc.*)

- Yes
- No

If Yes, describe what data or documents will be used and how they will be obtained:

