Data will include the following: 1. Behavioral data (events that occur in the system due to students interacting with the system; e.g., time spent logged on) 2. Self-report data (measures of engagement, user experience surveys, the PHQ and GAD7 scores). Participant data will be collected via the TheraGroup systems backend in the form of log data (Behavioral Data) or through Qualtrics (Depression and Anxiety scores, measures of engagement, user experience surveys).

Will recordings be made?

- Yes
- No

If Yes:

- Video Taping
- Audio Taping
- Mandatory Recording
- Voluntary Recording

Is the use of recordings detailed in the consent form?

- Yes
- No

Will recordings be retained?

- Yes
- No

If Yes, how long will records be retained before they are destroyed/erased?

Will any new specimens be collected? (i.e. *blood tissue, etc.*)

- Yes
- No

If Yes, describe what specimens will be used and how they will be obtained:

Does the experiment involve the use of human fluid, tissue and/or blood?

- Yes
- No

Will any invasive or sensitive procedures be done?

Yes No

If Yes, check all that apply:

- Blood Samples
- Physical Measurements (electrodes, etc)
- rDNA
- Stress Exercise
- Urine Samples
- Other, specify: _____

DOCUMENT RETENTION

Federal regulations require that human research documents be retained for a minimum of three years AFTER the completion of the study AND data analysis. Some disciplines or granting agencies require longer retention times.

Length of time retained after completion of study and data analysis:

At least three years

Person responsible for data retention (*If you are a student, please list faculty mentor*) & data storage location:

All data will be kept on a password protected computer in [name] office in [name].

OTHER COMPLIANCE ISSUES

If the study involves the use of **animals, infectious biohazards (e.g. blood), and/or recombinant DNA**, it is required that approval be granted for the use of such through the appropriate compliance committee.

SIGNATURE ASSURANCES

PRINCIPAL INVESTIGATOR

I understand Prairie View A&M University's procedures concerning research involving human subjects and **by initialing** below, I certify:

AL I have read The Belmont Report "Ethical Principles and Guidelines for the Protection of Human Subjects of Research" and subscribe to the principles it contains.

AL I accept responsibility for the scientific and ethical conduct of this research study.

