Statistical Analysis Plan

Official Study Title: Guided group telehealth to deliver evidence-based therapeutic care to Black college students

NCT Number:

Date of Document: 03/10/2025

Statistical Analysis Plan

To test the primary hypothesis that participants in the Guided Group Telehealth (GGT) condition will experience reductions in depression and anxiety comparable to those in the Individual Telehealth (IT) condition, we will use a mixed-design repeated measures ANOVA. The within-subjects factor will be time (baseline, week 4, week 8, and week 12), and the between-subjects factor will be therapy condition (GGT vs. IT). The dependent variables will be PHQ-9 and GAD-7 scores, measuring depression and anxiety, respectively. Interaction effects will be examined to assess whether changes in symptom severity over time differ between the two conditions. For secondary analyses, we will use independent samples t-tests to compare user engagement and user experience scores between the two conditions at week 12. Descriptive statistics will be used to summarize engagement data, including participation rates, message frequency, and task completion. Additionally, qualitative analysis will be conducted on open-ended responses from the user experience survey to identify common themes related to participants' satisfaction and perceived effectiveness of the intervention. All analyses will be conducted using an alpha level of 0.05, and effect sizes will be reported alongside p-values. If violations of normality or sphericity are detected, appropriate corrections, such as Greenhouse-Geisser adjustments or nonparametric alternatives, will be applied.

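### The SAP has no term for therapy group: the week-12 t-test exceeds alpha 0.05 if scores correlate within groups, the condition-by-time test only if change from baseline does

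*SAP*

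**What the plan says.** The Protocol (Purpose of Study) describes GGT as "one mental health counselor to many students" and IT as one-to-one. Under Procedures, the group arm alone adds "asynchronous communication with peers struggling with similar issues". Subject Recruitment gives "Maximum anticipated sample size: 200".

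The SAP tests the primary hypothesis with a mixed repeated-measures ANOVA on PHQ-9 and GAD-7 over baseline and weeks 4, 8 and 12, in which "the between-subjects factor will be therapy condition (GGT vs. IT"). Differing change is judged by the interaction. Week-12 engagement and experience scores are compared by independent-samples t-tests. Alpha is 0.05 throughout, and corrections are foreseen only for non-normality and non-sphericity.

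Neither document states group size, number of groups, fixed or rolling membership, number of counselors, an ICC or the allocation ratio.

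**The concern.** Both planned tests treat students as independent. In GGT, members of one group share a counselor and talk to each other, so their outcomes may move together. If they do, the GGT mean is less precise than the analysis assumes, and GGT-IT differences are declared too often.

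That works against the sponsor's own hypothesis of comparable reductions. The Purpose of Study section makes later work depend on the result, under the condition "If outcome measures in the GGT group are in line with outcome measures in the IT group". A feasibility study is also the natural place to estimate the ICC that a follow-on trial would need, and the plan would not produce one.

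**Working it through.** **Inputs from the documents.** Alpha 0.05; four visits; maximum 200 participants; first assessment before therapy starts (Protocol, compensation table).

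**Assumptions.** Two-sided tests; equal allocation with 96-100 analysed per arm; IT unclustered; within-person correlation 0.5; group size m from 5 to 20; ICC from 0.01 to 0.10.

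**1. Nominal level.** With no group effect, the formula in step 2 returns 0.050 and the simulated interaction test rejects 4.9-5.1%.

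**2. Week-12 t-test.** The variance of the GGT mean is multiplied by 1 + (m-1) × ICC. Averaged over two equal arms, the variance of the difference is multiplied by r = 1 + (m-1) × ICC/2. Actual alpha = 2 × P(Z > 1.96/√r).

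| m | ICC | r | actual alpha |
|---|---|---|---|
| 8 | 0.01 | 1.035 | 5.4% |
| 8 | 0.05 | 1.175 | 7.1% |
| 8 | 0.10 | 1.35 | 9.2% |
| 20 | 0.01 | 1.095 | 6.1% |
| 20 | 0.05 | 1.475 | 10.7% |
| 20 | 0.10 | 1.95 | 16.0% |

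**3. Why the interaction test differs.** Let group g add u_g × w_t at visit t. The interaction uses deviations from each student's mean over time, so the group contributes u_g × (w_t - mean of w). With w = 1, 1, 1, 1 this is zero at every visit and the effect cancels. With w = 0, 1/3, 2/3, 1 (growing) or 0, 1, 1, 1 (in full from week 4) it does not. Because baseline precedes therapy, similarity produced by the group can arise only afterwards, that is, as correlated change.

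**4. Planned interaction test by simulation** (20,000 replicates per cell, rejection under no true difference):

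| m, pattern | ICC 0.01 | 0.02 | 0.05 | 0.10 |
|---|---|---|---|---|
| 5, growing | 5.2% | 5.3% | 5.6% | 6.6% |
| 8, growing | 5.4% | 5.3% | 6.2% | 7.6% |
| 10, growing | 5.1% | 5.6% | 6.6% | 8.8% |
| 20, growing | 6.0% | 6.4% | 8.9% | 13.1% |
| 8, full from week 4 | 5.3% | 5.6% | 7.0% | 8.9% |
| 20, full from week 4 | 6.0% | 7.0% | 10.1% | 15.0% |

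With a constant group effect every cell lies at 4.8-5.4%. A separate simulation (4,000 replicates) gave the same picture: for m = 20 and ICC 0.10, 12.8% growing, 16.2% in full from week 4, and 4.9% constant. There the Greenhouse-Geisser adjustment lowered rejection by at most about 0.3 points, as expected, since it concerns correlation within a student and not between students.

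**The case against.** The strongest reply is that the size rests on values the documents do not give. For groups of 5-10 at ICC 0.01-0.02 the primary test stays at or below 5.6%. Contact is asynchronous, by text and under made-up names, so strong group effects cannot be presumed. 200 is a maximum, and dropout leaves fewer analysed members per group and a smaller design effect. All of this stands, and it limits the size of the problem. It does not justify an unstated independence assumption in an arm built on shared interaction.

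Four stronger readings are tempting and are not supported:

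- A reader might infer that any within-group correlation invalidates the primary test. It does not; a constant effect cancels.
- A reader might infer that the go-forward decision hangs on a p-value. The Purpose of Study sentence is cut off in the available text and names no test.
- A reader might infer that group membership is not recorded. The documents say only that "Participant data will be collected via the TheraGroup systems backend in the form of log data (Behavioral Data) or through Qualtrics" and that "participants use a name they make up for the purpose of the group only to ensure they remain anonymous". Whether the two sources can be linked is left open.
- A reader might infer that the correction costs 10 to 15 points of power, by setting it against the 65% and 63% rejection of a baseline-adjusted test that ignores groups. The SAP does not plan that test, and its type I error here is 7.8% (ICC 0.05) and 10.3% (ICC 0.10).

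**Conclusion.** The concern holds in conditional form. The analysis has no term for therapy group or therapist, and none of its listed corrections fills the gap. The week-12 t-test is too liberal if scores correlate positively within groups. The condition-by-time test is too liberal only if change does, which is plausible because baseline precedes therapy.

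The effect is small for small groups with low ICC. For groups of 8-10 at ICC 0.05 it is modest: 6.2-6.6% for the interaction test with a growing effect. It is material for groups of 20 or ICC near 0.10. These figures assume about 100 analysed per arm, the most that equal allocation allows, and no clustering in IT. The sponsor should fix this before analysis.

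The correction also makes non-significance more likely. A reader might take a non-significant corrected test as evidence of comparability; a difference test without a margin does not supply that.

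**What to change.** 1. Record therapy-group and therapist identifiers and confirm that both link to each Qualtrics outcome record. State group size, number of groups, and whether membership is fixed or rolling.
2. For PHQ-9 and GAD-7, name one primary model: a baseline-adjusted GGT-IT comparison at week 12, with a random group effect in GGT only and Satterthwaite or Kenward-Roger degrees of freedom. In simulation with a growing effect and ICC 0-0.10 it rejected 4.2-5.2% with 12 groups of 8 and 3.6-5.7% with 5 groups of 20. If the four-visit interaction is kept, include random group and group-by-time effects in GGT; a group intercept alone does not reach correlated change.
3. Use the same GGT-only group effect for the week-12 engagement score. Apply it to user experience only if a numeric score is defined, since the listed experience items are open-ended.
4. Report the ICC. If only one or two groups run, state that group and condition effects cannot be separated; with 2 groups of 20 the model in item 2 still rejected up to 8.8%.

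**Cost.** SAP wording and the linking of two identifiers, with no extra participants. Standard errors widen and degrees of freedom fall. For groups of 8 without baseline adjustment, the week-12 standard error grows by √1.175 - 1 = 8% at ICC 0.05 and √1.35 - 1 = 16% at ICC 0.10.

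Rejection at a true 0.3 SD week-12 difference (12 groups of 8, within-person correlation 0.5 assumed):

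| Test | Rejection |
|---|---|
| Model in item 2 | about 55% (ICC 0.05), 48% (ICC 0.10) |
| Planned interaction test | about 42-44% |
| Unadjusted week-12 t-test | about 53-55% |

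The last two exceed 0.05 under the null here, so their rejection rates are flattered. No rejection rate at this difference was calculated for the four-visit interaction with group-by-time effects.

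### The primary hypothesis says group and individual telehealth are comparable, but the plan tests only for a difference and never defines comparable

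*SAP*

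**What the plan says.** The SAP is a single paragraph. It says it will test a primary hypothesis, namely that GGT participants "will experience reductions in depression and anxiety comparable to those in the Individual Telehealth (IT) condition". The method is a mixed-design repeated measures ANOVA with time (baseline, weeks 4, 8 and 12) and condition as factors, applied to PHQ-9 and to GAD-7. The between-arm question is put this way: "Interaction effects will be examined to assess whether changes in symptom severity over time differ between the two conditions". On inference it adds: "All analyses will be conducted using an alpha level of 0.05, and effect sizes will be reported alongside p-values".

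The Protocol (Purpose of Study) ties the next step to the same kind of claim: "If outcome measures in the GGT group are in line with outcome measures in the IT group", then "the feasibility study will serve as a precursor to testing the effects". That sentence is cut off in the available text. Subject Recruitment gives a maximum anticipated sample size of 200, without a derivation.

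Neither document states a margin, a confidence interval for the difference between arms, an equivalence or non-inferiority test, the direction of the claim, or whether both scales must meet it.

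**The concern.** The null hypothesis of the interaction test is that the two arms change in parallel, which is close to what the investigators hope to show. Rejecting it could contradict the hypothesis. Failing to reject it may mean the arms are similar, or only that the data are too few or too variable to tell. The plan has no rule that separates the two.

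At stake is the main conclusion of the study and the decision that the Protocol attaches to it. A non-significant interaction is the result most easily mistaken for agreement with the hypothesis, and it becomes likelier as the analysed sample shrinks. The SAP does not say how missing assessments are handled. If only participants with all four assessments are analysed (an assumption), dropout pushes the result that way through the smaller sample. Informative or unequal dropout could act in either direction.

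**Working it through.** The plan states no power, margin, SD or retention, so there is no figure of its own to reproduce. The finding rests on setting claim against test. The arithmetic below only shows its size.

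**1. Claim against test**

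| Result of the planned ANOVA | What it says about comparable |
|---|---|
| Interaction significant | May count against it; with no margin, even a trivial difference could do so |
| Interaction not significant | Not established; compatible with similarity or with low power |
| Effect size reported | No interval or threshold attached, so no decision follows |

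**2. How often a real deficit would go undetected**

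From the documents: four assessments, alpha 0.05, at most 200 participants. Assumed: SD 5, within-person correlation 0.6, 1:1 split, no clustering, and a GGT deficit of 0, 0.67, 1.33 and 2.0 points at the four visits.

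- Centred deficits are -1, -1/3, 1/3 and 1; their squares sum to 2.222.
- Noncentrality = (n/2) × 2.222 / (SD² × (1 - correlation)) = (n/2) × 2.222 / (25 × 0.4) = 0.1111n.
- Degrees of freedom are 3 and 3(2n - 2).

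| Analysed per arm | Noncentrality | Non-significant | SD 4 to 6 | Correlation 0.7 to 0.4 |
|---|---|---|---|---|
| 100 | 11.11 | 19.5% | 5-37% | 9-39% |
| 70 | 7.78 | 36.4% | 16-53% | 23-55% |
| 50 | 5.56 | 52.1% | 31-66% | 39-67% |

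These figures are for one scale. No figure is given for both, because entry needs a score of 5 on only one of them, so an equal deficit on both cannot be assumed. A separate simulation of the interaction test in SD units (correlation 0.5, linear growth) points the same way: a true week-12 difference of 0.4 SD is missed 30% of the time with 100 per arm and 61% with 50.

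**3. Precision if the aim becomes estimation**

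SE = SD × √(1 - 0.6²) × √(2/n) = 5 × 0.8 × √(2/n); half-width = 1.96 × SE.

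| Per arm | SE | 95% half-width | SD 4 to 6 | Correlation 0.7 to 0.4 |
|---|---|---|---|---|
| 100 | 0.566 | 1.11 | 0.9-1.3 | 1.0-1.3 |
| 70 | 0.676 | 1.33 | 1.1-1.6 | 1.2-1.5 |
| 50 | 0.800 | 1.57 | 1.3-1.9 | 1.4-1.8 |

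GGT is "group text based therapy (one mental health counselor to many students") and includes "asynchronous communication with peers struggling with similar issues", so outcomes within a group may be correlated. With assumed groups of 10 and ICC 0.05 to 0.10 in GGT only, the design effect is 1 + 9 × ICC = 1.45 to 1.90. The SE grows by √((1 + 1.45)/2) = 1.107 to √((1 + 1.90)/2) = 1.204, that is 11-20%.

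**4. Power if a comparability claim is kept**

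Both scales must succeed. Assumed: true difference 0, correlation between the two estimates 0 to 0.6, no clustering, 95% intervals. With z = margin/SE - 1.96, power is P(both Z < z) for non-inferiority and P(both |Z| < z) for equivalence.

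| Margin (assumed) | Per arm | Non-inferiority | Equivalence |
|---|---|---|---|
| 2.0 points | 100 | 89-90% | 78-81% |
| | 70 | 71-75% | 47-51% |
| | 50 | 50-58% | 17-20% |
| 1.5 points | 100 | 57-64% | 26-30% |
| | 70 | 36-46% | 4-5% |
| | 50 | 22-32% | 0% |

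Number per arm for 80% joint power:

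| Margin | SD | Non-inferiority | Equivalence |
|---|---|---|---|
| 2.0 | 4 | 50-53 | 64-66 |
| 2.0 | 5 | 77-83 | 99-103 |
| 2.0 | 6 | 111-119 | 143-148 |
| 1.5 | 4 | 88-94 | 113-117 |
| 1.5 | 5 | 137-147 | 176-183 |
| 1.5 | 6 | 198-212 | 254-263 |

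At 2.0 points and SD 5, a within-person correlation of 0.7 to 0.4 moves the equivalence requirement from about 79 to about 135 per arm. A 90% interval, the usual match to alpha 0.05 for equivalence, lowers it from 99-103 to 82-86. With the clustering above allowed for, power at 2.0 points and 100 per arm falls to 70-83% (non-inferiority) and 45-65% (equivalence). If that clustering is ignored, the wrong-claim rate at the margin rises from 2.5% per scale to Φ(-1.96/1.107) = 3.8% up to Φ(-1.96/1.204) = 5.2%.

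**The case against.** The Protocol calls this a feasibility study, effect sizes are promised, and the SAP never says that a non-significant interaction will be read as comparability. A reader could compute an interval afterwards and judge it sensibly.

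All of that is true, but none of it repairs the plan. The SAP explicitly undertakes to test a primary hypothesis. If non-significance is not the criterion, there is none, and one chosen after the results are seen is not a test. The feasibility label is a good reason to make the aim estimation, not to leave claim and test mismatched.

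Three objections about detail stand. The 95% interval for equivalence is stricter than the common 90% convention, so part of its cost is a choice. A 1.5-point margin is out of reach within 200 at SD 5, but not for non-inferiority at SD 4. Using week 12 and baseline adjustment is also a choice; the SAP names week 12 only for its "independent samples t-tests to compare user engagement and user experience scores between the two conditions at week 12". These bear on the optional claim and the form of the remedy, not on the finding.

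**Conclusion.** The concern holds and must be fixed. Followed exactly, the plan can produce evidence against its primary hypothesis but none that confirms it. This follows from the text and needs no assumed figure.

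The size is illustrative. With a true deficit reaching 2.0 points, the planned test would be non-significant in about one trial in five with 100 analysed per arm and in about half with 50. That rests on SD 5, correlation 0.6, a 1:1 split and no clustering. The documents give none of these, and the ranges above show how far the result moves.

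**What to change.** Amend the SAP before results by arm are seen.

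**Recommended: estimation.** Restate the primary aim as estimating the baseline-adjusted GGT minus IT difference at week 12, with a 95% confidence interval for each scale that allows for correlation within GGT groups. State that a non-significant interaction will not be called comparability, and keep the ANOVA as descriptive. The cost is SAP wording only. The expected half-width is about 1.1 to 1.6 points with 100 down to 50 per arm, or 1.2 to 1.9 with the assumed clustering.

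**Optional: a comparability claim.** The sponsor states equivalence or non-inferiority and justifies a margin in points for each scale. Success requires, on both PHQ-9 and GAD-7, the whole 95% interval inside plus or minus the margin (equivalence), or its unfavourable limit within the margin (non-inferiority). Requiring both scales needs no alpha adjustment. If a 90% interval is preferred for equivalence, the SAP should say so in advance. The 2.5% wrong-claim rate per scale holds only if allocation is random (the Protocol says only that participants are assigned), clustering is handled and dropout is not informative. Within 200 participants this route is realistic only with a wide margin and good retention; otherwise use the first.

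### The hypothesis of comparable reductions is tested only by an unsigned 3-df time-by-condition interaction, with no signed arm difference, time point or confidence interval named for PHQ-9 or GAD-7

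*SAP*

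**What the plan says.** The SAP's primary hypothesis is that GGT participants "will experience reductions in depression and anxiety comparable to those in the Individual Telehealth (IT) condition". To test it, "we will use a mixed-design repeated measures ANOVA", with four time points (baseline and weeks 4, 8 and 12) and two conditions, on PHQ-9 and GAD-7. The term that carries the question is the interaction: "Interaction effects will be examined to assess whether changes in symptom severity over time differ between the two conditions". On reporting, the SAP adds: "All analyses will be conducted using an alpha level of 0.05, and effect sizes will be reported alongside p-values".

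For the two symptom scales it goes no further. It names no primary time point, no between-arm difference, no confidence interval and no margin. Week 12 is singled out only in the secondary analyses, where t-tests are used "to compare user engagement and user experience scores between the two conditions at week 12".

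The protocol, under Purpose of Study, says what the result is for: "If outcome measures in the GGT group are in line with outcome measures in the IT group", this feasibility study leads on to further testing.

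**The concern.** A claim that GGT is about as good as IT needs a statement of how much less, if at all, GGT reduces scores. The interaction F-test does not supply it. It asks whether the two four-point profiles are parallel. A significant result could mean that GGT is worse, that GGT is better, or that the arms parted briefly and met again. A non-significant result says only that non-parallelism was not detected.

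An effect size reported beside the p-value need not help. The SAP does not say which kind. The usual one for an interaction, partial eta-squared, has no sign and is not in PHQ-9 or GAD-7 points.

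The step to a further study rests on GGT matching IT. If the SAP is followed as written, a non-significant interaction could be read as support for that step even though it leaves the possible shortfall unbounded.

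**Working it through.** **No figure to reproduce.** The documents give no power, effect size, SD, correlation, dropout or derived sample size. The protocol (Subject Recruitment) gives only a maximum of 200, with no allocation ratio.

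**Inputs.**
- From the SAP: 4 times, 2 arms, alpha 0.05. Interaction df = (4 − 1)(2 − 1) = 3.
- Assumed: SD 5 on each scale, equal correlation r = 0.6 between any two visits, 1:1 allocation with n = 100 per arm (70 as a lower case), complete data, arms equal on average at baseline, no clustering within therapy groups, two-sided tests.

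**Formulas.** Let d_t be the arm gap at time t.
- Omnibus: noncentral F with 3 and 3(2n − 2) df, λ = (n/2) × Σ(d_t − mean d)² / [SD²(1 − r)]. At n = 100 this is 50 × Σ / 10 = 5 × Σ.
- Change from baseline to week 12: variance 2 × SD²(1 − r) = 20 per person, SE = √(2 × 20/100) = 0.632.
- Baseline-adjusted week 12: variance SD²(1 − r²) = 16 per person, SE = √(2 × 16/100) = 0.566.

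**Step 1: does significance mean a difference at the end of therapy?** Take gaps of 0, 2, 0, 0. The mean is 0.5, Σ = 3 × 0.25 + 2.25 = 3 and λ = 15. Power is about 92%, although the arms are equal at week 12. Reversing the sign of every gap leaves λ unchanged.

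**Step 2: how often is a 1.5-point week-12 gap missed?**
- Linear (0, 0.5, 1, 1.5): Σ = 1.25, λ = 6.25.
- Week 12 only (0, 0, 0, 1.5) or full from week 4 (0, 1.5, 1.5, 1.5): Σ = 1.6875, λ = 8.44.
- Change contrast: 1.5/0.632 = 2.37. Adjusted contrast: 1.5/0.566 = 2.65.

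| Shape, n per arm | Omnibus misses | Change misses | Adjusted misses |
|---|---|---|---|
| Linear, 100 | 47% | 34% | 25% |
| Week 12 only, or full from week 4, 100 | 32% | 34% | 25% |
| Linear, 70 | 61% | 50% | 40% |
| Week 12 only, or full from week 4, 70 | 49% | 50% | 40% |

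Range over r = 0.4, 0.5, 0.6, 0.7 (n = 100):
- Omnibus, linear gap: 63, 56, 47, 33%.
- Omnibus, week 12 only: 51, 43, 32, 19%.
- Change: 51, 44, 34, 22%.
- Adjusted: 37, 32, 25, 16%.

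**Step 3: what would the interval look like?** The half-width for the adjusted week-12 difference is 1.97 × 0.566 = 1.1 points at 100 per arm. At 70 per arm it is 1.98 × √(2 × 16/70) = 1.98 × 0.676 = 1.3 points.

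**Step 4: what does a week-12 contrast give up?** Take a gap of 1.5 points at week 4 that shrinks to a third by week 12 (0, 1.5, 1, 0.5). Σ is again 1.25 and λ is 6.25, so the omnibus misses 47%. The adjusted contrast has 0.5/0.566 = 0.88 and misses about 86%.

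**The case against.** **Power.** A reader might infer that the omnibus test always misses a week-12 gap more often than a single contrast. The figures do not support that. The linear gap is an unfavourable shape for the omnibus. For a gap at week 12 only, or one that opens by week 4 and persists, it misses 32% against 34% for plain change. An unadjusted week-12 t-test, the type the SAP uses for its secondary outcomes, misses 44%. In those shapes the whole gain comes from adjusting for baseline. It can also be small: in a simulation with a 0.4 SD gap, 100 per arm and AR(1) correlation 0.7, a week-12-only gap gave the omnibus 83% power and the adjusted contrast 85%. This objection stands, and the power comparison is a supporting argument only.

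**Size and direction.** A reader might also infer that the analysis reports no size at all. The SAP does promise effect sizes, the arm-by-time means would show direction, and nothing rules out follow-up contrasts. What remains is that the type of effect size is unstated and no signed difference with an interval is planned.

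**Week 12.** The SAP asks about change over time and does not itself declare week 12 the primary time for the symptom scales. Choosing the end of the 12-week therapy is a judgement, and step 4 shows what it costs.

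**Margin.** A contrast alone does not establish comparability, because an interval needs a margin to be judged against. That is right. Equally, a margin can only be applied to a signed difference with an interval, so naming that difference is a necessary step.

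**Conclusion.** The point holds as a gap in specification. The primary question is one of similarity, and the only test named for it is unsigned, reacts to any profile difference and puts no bound on how much worse GGT could be. That conclusion follows from the SAP's text and needs no assumed numbers.

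The sizes do rest on assumptions (SD 5, r 0.6, 1:1 allocation, complete data, equal baselines, no clustering). A week-4-only gap of 2 points would be significant about 92% of the time at 100 per arm. A 1.5-point week-12 gap would be missed by the omnibus 47% or 32% of the time depending on shape, by plain change 34%, and by the baseline-adjusted contrast 25%. Only the adjusted contrast beats the omnibus in each of these shapes, and all of them have the full gap at week 12.

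A reader might go on to conclude that the sponsor will treat non-significance as proof of comparability. The SAP gives no decision rule, so the documents leave that open without stating it.

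**What to change.** In the SAP, name the GGT-minus-IT difference at week 12, adjusted for the baseline score, as the primary contrast for PHQ-9 and for GAD-7, each with a 95% confidence interval in scale points. State that the comparability conclusion rests on that interval against a margin that the sponsor fixes and justifies before analysis. Keep the omnibus interaction and the week-4 and week-8 contrasts as supportive, and say which effect size accompanies each test.

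The cost is SAP wording plus the work of agreeing a margin, with no new visits or data. The expected half-widths of about 1.1 points (100 per arm) or 1.3 (70 per arm), under the assumptions above, show how fine a margin the study could address. The downside is that a gap which is largest early and fades by week 12 would be seen mainly in the supportive analyses (about 86% missed by the primary contrast, against 47% by the omnibus, in the example worked). The SAP should say how such a finding will be reported.
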